10.5 Investigator Communications with Pfizer

All Serious Adverse Events must be reported to Pfizer Clinical Trial Department

- All SAEs, whether related or unrelated to avelumab and all pregnancies must be reported to Pfizer (by the investigator or designee) within 24 hours.
- All SAEs should be reported via confirmed facsimile (fax) transmission, or scanned and reported via electronic mail to:
- **SAEs may be submitted directly via email.**

SAE Email Address: [contact]

SAE [contact]

11.0 STATISTICAL CONSIDERATIONS

This will be a single arm, single center, open label study of avelumab in combination with 5-azacytidine in patients with refractory, relapsed or untreated AML.

11.1 Sample Size

Part a. Lead-in phase IB

The primary objective of the lead-in phase is to determine the MTD and DLT of avelumab in combination with 5-azacytidine in patients with refractory/ relapsed AML during the first cycle (28 days). 12 - 18 participants will be accrued into lead-in part of the study.

Once safety of the MTD has been established, any patients still on study at a dose lower than MTD can be dose escalated up to MTD.

Part b. Phase II

The primary objective of the phase II is to determine the efficacy of avelumab in combination with 5-azacytidine in patients with refractory/relapsed or untreated AML. The efficacy of the combination will be measured by the overall response rate (ORR), defined as CR (complete remission) + CR_p (complete remission with incomplete platelet recovery) + CR_i (complete remission with incomplete count recovery) + PR (partial response) + morphologic leukemia free state (MLFS)+HI within 3 months of treatment initiation among adult patients with refractory/ relapsed AML. ORR and toxicity will be monitored simultaneously using the Bayesian approach of Thall, Simon, Estey (1995, 1996) and the extension by Thall and Sung (1998).

Up to 40 additional patients (excluding patients treated at the MTD from the lead-in part) will be recruited for the Phase II part.

Total accrual: 12-18 patients from lead-in + 40 Phase II patients (N= 52 - 58 patients)

11.2 Statistical Design

Part a. Lead-in phase IB

The MTD is defined as the highest dose level with ≤ 1 out of 6 patients experience a DLT during the first 28 days of treatment. DLT is defined in section 5.2.2. The dosing schema for the combination treatment during the lead in phase is shown in Table 1 in section 5.2.1.

A Toxicity Summary will be submitted to the IND Office Medical Monitor, after the first three evaluable patients have completed their first cycle, and every three evaluable patients thereafter, prior to dose modification, expansion, or phase II initiation.

Part b. Phase II

An Efficacy/Toxicity Summary will be submitted every five evaluable patients during Phase II.

The historical experience in relapsed/refractory AML patient population is that historical responses (CR/CRp/CRi/PR/Hi/MLFS with >50% blast reduction) with single agent hypomethylator therapy (5-azacytidine or decitabine) or with hypomethylator combinations (azacytidine+revlimid, decitabine+myelotarg, azacytidine+vorinostat, decitabine+valproate) investigated at MDACC over the last 10 years are 10% ([name], Kantarjian H et al., European Hematology Association Conference, June 2016). The target ORR with the experimental treatment is 30%. This regimen of the combination treatment will be considered worthy of further investigation if it elicits an increase in ORR to 30% with acceptable toxicity. A >30% drug-related grade 3/4 toxicity rate is considered unacceptable. Thus, interim monitoring rules, assuming the prior distributions above, were constructed that meet the following two conditions,

- 1) Stop if $\text{Prob}\{p(\text{ORR}, E) < p(\text{ORR}, H) + 0.20 \mid \text{data}\} > 0.975$, or
- 2) Stop if $\text{Prob}\{p(\text{TOX}, E) > 0.30 \mid \text{data}\} > 0.975$,

where $P(\text{ORR}, E)$ and $P(\text{TOX}, E)$ are the true ORR and toxicity rates for the combination treatment, and $p(\text{ORR}, H)$ is the true ORR rate of the standard treatment. The first rule provides for stopping the study if the data suggest that it is unlikely (i.e., probability < 2.5%) that ORR rate of the combination treatment is greater than the ORR rate of standard treatment by 20.0%. The second condition will stop the study early if excessive therapy-related grade 3/4 toxicity (>30%) is highly probable (i.e., probability >97.5%) for the combination treatment. Monitoring for toxicity and fertility will not begin until 5 patients have been evaluated, and cohort size for future evaluations is 5.

The monitoring rule for the toxicity rate, based on these assumptions and monitoring conditions above is found in Table 7. **For example, accrual will cease if 4 or more patients experience toxicities among the first 5 patients.**

Table 7. Stop accrual if the number of drug-related grade 3/4 toxicities is greater than or equal to indicated (i.e., # patients with toxicities) among the number of patients evaluated								
# patients evaluated	5	10	15	20	25	30	35	40
# patients with toxicities	4-5	7-10	9-15	11-20	13-25	15-30	17-35	Always stop

Monitoring the ORR rate, based on the above assumptions and monitoring conditions is found in Table 8. **For example, accrual will cease if no patients experience an overall response within 3 months of initiation of therapy in the first 10 patients treated.**

Table 8. Stop accrual if the number with overall response is less than or equal to indicated (i.e., # patients with overall response) among the number of patients evaluated							
# patients evaluated	5-10	15	20	25	30	35	40

# patients with overall response	0	0-1	0-2	0-3	0-4	0-5	Always stop
----------------------------------	---	-----	-----	-----	-----	-----	-------------

Multc Lean Desktop (version 2.1.0) was used to generate the toxicity and futility stopping boundaries and the OC table (Table 9). In order to utilize the software for the design, a beta (0.2, 1.8) was assumed for the experimental treatment response prior distribution and a constant rate of 10% for the standard treatment, respectively. For response stopping criterion, the shift parameter delta was 0.20. In addition, a 30% toxicity constant rate and beta (0.6, 1.4) priors were assumed for the standard treatment toxicity constant rate and experimental treatment toxicity prior distribution, respectively.

The probability of stopping the study early if the true ORR of the combination treatment was 30% and the true toxicity rate was 30% was 25%. Probabilities of stopping early for high true toxicity rates (i.e., 50%) were 45% when the true ORR was 30% and 95% when true ORR rate was 10%.

Table 9. Operating characteristics for simultaneous monitoring response and toxicity rates for patients treated with combination treatment

True Toxicity Rate	True ORR	Prob(stop the trial early)
0.10	0.10	0.9294
	0.20	0.5119
	0.30	0.2029
	0.40	0.0817
	0.50	0.0319
0.20	0.10	0.9300
	0.20	0.5156
	0.30	0.2090
	0.40	0.0887
	0.50	0.0393
0.30	0.10	0.9339
	0.20	0.5429
	0.30	0.2535
	0.40	0.1400
	0.50	0.0934
0.40	0.10	0.9512

Table 9. Operating characteristics for simultaneous monitoring response and toxicity rates for patients treated with combination treatment

True Toxicity Rate	True ORR	Prob(stop the trial early)
	0.20	0.6623
	0.30	0.4486
	0.40	0.3648
	0.50	0.3303
0.50	0.10	0.9803
	0.20	0.8637
	0.30	0.7774
	0.40	0.7436
	0.50	0.7297

Statistical Analysis Plan

All patients who received any dose of the study agent will be included in the analysis for efficacy and safety. Demographic/clinical characteristics (including duration of response) and safety data of the patients will be summarized using descriptive statistics such as mean, standard deviation, median and range. For the primary efficacy analysis, we will estimate the ORR for the combination treatment, along with the 95% credible interval. For the efficacy, a sample size of 40 patients ensures a posterior 95% credible interval for ORR of (0.17, 0.43), if the trial is not terminated early, under the assumption of a 30% ORR. Patients who drop out of the study before completing all the cycles will be treated as “failures” for the primary analysis. ORR during the study period will also be presented with the 95% confidence credible. The association between ORR and patient’s clinical characteristics will be examined by Wilcoxon’s rank sum test or Fisher’s exact test, as appropriate. Toxicity type, severity and attribution will be summarized for each patient using frequency tables.

The distribution of time-to-event endpoints (DFS and OS) including overall survival and progression free survival will be estimated using the method of Kaplan and Meier. Comparisons of time-to-event endpoints by important subgroups will be made using the log-rank tests. Paired t-tests will be used to determine the immunological and molecular changes in the peripheral blood and bone marrow from baseline to the time of response, and to the time of disease progression. Correlation analysis (such as logistic regression analysis) will be conducted to determine the relationship between induction of hypomethylation / DNA damage and clinical response.

A Toxicity Summary will be submitted to the IND Office Medical Monitor, after the first three patients have completed their first cycle of study therapy or administration is

discontinued, whichever comes first, and every three evaluable patients thereafter during the Lead-in Phase IB.

An Efficacy/Toxicity Summary will be submitted every five evaluable patients during **Phase II**.

Statistical analysis of biomarker data: Descriptive statistics including plots, mean, median and standard deviations will be used to summarize data. For continuous outcomes, t-test and ANOVA will be used to compare outcome measures across patient characteristics. Dunnett's and Tukey's test that properly adjust for multiplicity in multiple tests will be implemented. Pairwise comparisons will be performed using pre- and post-therapy samples from each patient. The chi-square test or Fisher's exact test will be used to test the association between two categorical variables such as disease state and performance status. Both univariate and multivariate logistic regressions will be performed to model prognostic factors.

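### Section 11.2 gives early-stopping probabilities of 45% and 95% at 50% true toxicity; those are Table 9's values for 40% toxicity, and at 50% the design gives 78% and 98%.

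*Combined protocol and SAP*

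**What the plan says.** Section 11.2, Part b, monitors response and toxicity together in phase II and summarises the operating characteristics in two sentences placed before Table 9.

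- The first concerns 30% toxicity with 30% ORR. It gives the probability of stopping early when the "true ORR of the combination treatment was 30% and the true toxicity rate was 30% was 25" per cent.
- The second concerns high toxicity: "Probabilities of stopping early for high true toxicity rates (i.e., 50%) were 45% when the true ORR was 30" per cent, "and 95% when true ORR rate was 10" per cent.

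Table 9 ("Operating characteristics for simultaneous monitoring response and toxicity rates for patients treated with combination treatment") then gives the probability of stopping early for five toxicity rates crossed with five response rates. The cells that matter here are:

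| True toxicity | ORR 0.10 | ORR 0.30 |
|---|---|---|
| 0.30 | 0.9339 | 0.2535 |
| 0.40 | 0.9512 | 0.4486 |
| 0.50 | 0.9803 | 0.7774 |

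**The concern.** The second sentence labels its figures as belonging to 50% toxicity, but they match the 40% block of Table 9. With all 25 cells rounded to whole per cent, 45 occurs once and 95 occurs once. Both are at toxicity 0.40, at exactly the two response rates the sentence names. The first sentence matches its own cell (0.2535, or 25%), so the slip is confined to the second.

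Section 11.2 treats a drug-related grade 3/4 rate above 30% as unacceptable, and this sentence is the only prose account of how the monitoring performs above that limit. Someone judging the safety monitoring from the text would conclude that, at the target ORR of 30%, a regimen toxic in half of patients gets past every interim look more often than not. The design does not behave that way. A reader who notices the disagreement with Table 9 cannot tell from the page alone which of the two to trust.

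**Working it through.** **Inputs, all from Section 11.2 except the sample size**

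- Response: "a beta (0.2, 1.8) was assumed for the experimental treatment response prior distribution and a constant rate of 10% for the standard treatment"; required gain 0.20, so the comparison value is 0.10 + 0.20 = 0.30.
- Toxicity: Beta(0.6, 1.4) prior, fixed comparison rate 0.30.
- Posterior cut-off for both rules: 0.975.
- First look at 5 patients, then every 5; maximum 40 (Section 11.1). Early stopping therefore means stopping at n = 5, 10, ..., 35.

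**Step 1: reproduce the boundaries (Tables 7 and 8)**

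With x responses and y toxicities among n patients:

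- stop for futility if P(p < 0.30) > 0.975, where p ~ Beta(0.2 + x, 1.8 + n − x);
- stop for toxicity if P(p > 0.30) > 0.975, where p ~ Beta(0.6 + y, 1.4 + n − y).

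| n | 5 | 10 | 15 | 20 | 25 | 30 | 35 |
|---|---|---|---|---|---|---|---|
| Stop if toxicities ≥ | 4 | 7 | 9 | 11 | 13 | 15 | 17 |
| Stop if responses ≤ | 0 | 0 | 1 | 2 | 3 | 4 | 5 |

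These agree with Tables 7 and 8 at every look.

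**Step 2: reproduce Table 9**

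An exact binomial recursion over the seven looks gives the probability of never crossing each boundary: S_T(t) for true toxicity t and S_R(r) for true ORR r. With response and toxicity independent,

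P(stop early) = 1 − S_T(t) × S_R(r).

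All 25 cells are reproduced; the largest absolute difference is 0.00005. The cell quoted correctly in the text (toxicity 0.30, ORR 0.30) comes out at 0.2535.

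**Step 3: the two rates in dispute**

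The toxicity rule alone stops early with probability 0.7209 at t = 0.50 and 0.3086 at t = 0.40, so S_T = 0.2791 and 0.6914. The futility rule alone stops early with probability 0.2025 at ORR 0.30, so S_R = 0.7975. At ORR 0.10, Table 9 itself implies S_R = (1 − 0.9803)/0.2791 = 0.0706.

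- t = 0.50, ORR 0.30: 1 − 0.2791 × 0.7975 = 0.7774
- t = 0.50, ORR 0.10: 1 − 0.2791 × 0.0706 = 0.9803 (full recursion: 0.9803)
- t = 0.40, ORR 0.30: 1 − 0.6914 × 0.7975 = 0.4486
- t = 0.40, ORR 0.10: 1 − 0.6914 × 0.0706 = 0.9512 (full recursion: 0.9512)

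**Step 4: compare with the text**

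| At 50% toxicity | Text | Design | Difference |
|---|---|---|---|
| Stops early, ORR 30% | 45% | 78% | 33 points |
| Stops early, ORR 10% | 95% | 98% | 3 points |
| Does not stop early, ORR 30% | 55% | 22% | 33 points |
| Does not stop early, ORR 10% | 5% | 2% | 3 points |

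**Step 5: could another reading rescue the text?**

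At 50% toxicity:

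- futility looks starting at n = 10: 0.744 (ORR 30%) and 0.975 (ORR 10%);
- both rules starting at n = 10: 0.731 and 0.973;
- toxicity rule alone: 0.721.

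None gives 45% with 95%. Since the toxicity rule alone already stops the trial 72% of the time, adding a second stopping rule cannot bring the total down to 45%.

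**The case against.** The best case on the other side accepts the mismatch and argues that it is editorial. The trial would be run from the two posterior conditions and Tables 7 and 8, all of which are right. The sentence only summarises Table 9, where the correct values appear. The error makes the design look weaker than it is, so it does not hide a risk, and at ORR 10% the gap changes no conclusion. All of this stands, and it limits the weight of the point. It does not make the sentence correct: the ORR 30% figure is 33 points off at the rate named.

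It can also be argued that the author may have meant 40% and mistyped the label, rather than reading from the wrong rows. That is fair. The documents do not show which happened, and either explanation leaves label and figures in disagreement.

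Finally, the chance of not stopping early is just one minus the stopping probability, so it is no further evidence. It also describes the formal rules only, since the Study Stopping Rules (Section 9.2) let the principal investigator and the IND office end the study at any time.

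**Conclusion.** The concern holds. At a true toxicity rate of 50% the design stops early with probability 78% at ORR 30% and 98% at ORR 10%, against the stated 45% and 95%. The stated figures are correct only for 40% toxicity. Tables 7, 8 and 9 agree with each other and with the stated inputs, so the error lies in this one sentence. The calculation assumes that response and toxicity are independent and does not count reaching 40 patients as early stopping; both are supported by the exact reproduction of all 25 cells. The sentence should be corrected because it misstates a safety operating characteristic, but stopping boundaries, sample size and trial conduct are unaffected.

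**What to change.** Correct the sentence in one of two ways, according to which rate the authors meant:

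- keep 50% toxicity and state 78% at ORR 30% and 98% at ORR 10%; or
- change the toxicity rate to 40% and keep 45% and 95%.

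The cost is one sentence, with no new simulation and no change to any table.

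A separate, minor query can be settled in one line at the same time. Table 7 is worded "Stop accrual if the number of drug-related grade 3/4 toxicities is greater than or equal to indicated", which read literally leaves out a drug-related death (grade 5), whereas the lead-in DLT definition (Section 5.2.1.3) lists treatment-related death. The sponsor should confirm whether such deaths count towards Table 7. The arithmetic above does not depend on the answer.

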An Open-label Phase Ib/II Study of Avelumab in Combination with 5-azacytidine (Vidaza) for the Treatment of Patients with Refractory/Relapsed Acute Myeloid Leukemia
2016-0444

Core Protocol Information

Short Title	Avelumab (antiPDL1) and azacytidine in AML
Study Chair:	[name]
Additional Contact:	[name] [name] Leukemia Protocol Review Group
Additional Memo Recipients:	Recipients List OPR Recipients (for OPR use only) None Study Staff Recipients None
Department:	Leukemia
[contact]
Unit:	428
Study Manager:	[name]
Full Title:	An Open-label Phase Ib/II Study of Avelumab in Combination with 5-azacytidine (Vidaza) for the Treatment of Patients with Refractory/Relapsed Acute Myeloid Leukemia
Public Description:	N/a
Protocol Type:	Standard Protocol
Protocol Phase:	Phase I/Phase II
Version Status:	Terminated 10/03/2019
Version:	15
Document Status:	Saved as "Final"
Submitted by:	[name]--8/13/2019 10:24:00 AM
OPR Action:	Accepted by: [name] -- 8/22/2019 9:13:02 AM

Which Committee will review this protocol?

- The Clinical Research Committee - (CRC)

Avelumab and 5_azacytidine in AML_IST_(Final) 7.27.2018.doc

Protocol Body

An Open-label Phase Ib/II Study of Avelumab in
Combination with 5-azacytidine (Vidaza) for the Treatment
of Patients with Refractory/ Relapsed Acute Myeloid
Leukemia

Principal Investigator: [name].

Co-PI: [name], M.D.

Sponsor: University of Texas, MD Anderson Cancer Center

IND number: 131967

University of Texas

MD Anderson Cancer Center

Leukemia Department, Unit

1.1 **OBJECTIVES**

1.2 **Primary Objectives**

Part a. Phase IB

To determine the maximum tolerated dose (MTD) and dose limiting toxicity (DLT) of avelumab in combination with 5-azacytidine in patients with refractory/ relapsed acute myeloid leukemia (AML).

Part b. Phase II

To determine the overall response rate (ORR) defined as complete remission (CR/complete remission with incomplete platelet recovery (CRp)/complete remission with incomplete count recovery (CRi)/partial remission (PR)/hematologic improvement (HI)/morphologic leukemia free state (MLFS) of avelumab in combination with 5-azacytidine in patients with refractory/ relapsed AML.

1.3 **Secondary Objectives:**

1. To determine the number of patients who achieve > 50% reduction in blasts on therapy with this combination.
2. To determine the duration of response, disease-free survival (DFS), and overall survival

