3. (OS) of patients with refractory/ relapsed AML treated with this combination.

1.4 **Exploratory Objectives:**

1. To study immunological and molecular features at baseline and at predefined time-points on-therapy with avelumab and azacytidine in the peripheral blood and bone marrow to include (a) quantify immune ligand expression by the AML blasts and AML stromal components (MDSCs and MSCs) including 4-1BBL, ICOSL, PD-L1, PD-L2, OX-40L, CD137L and (b) determine the quantitative expression of positive and negative co-stimulatory molecules on individual T-lymphocyte subsets including 4-1BB, CTLA-4, ICOS, PD-1, OX40, LAG-3 and TIM-3, and (c) identify the immunophenotype of tumor-infiltrating T-lymphocytes (TILs) pre- and post-therapy with the combination: CD8+, CD4+ effector, or CD4+ regulatory.
2. To develop a micro-array based gene expression profile (GEP) predictor of response to anti-PDL1 and epigenetic therapy in AML.
3. To determine the correlation of responses to the combination with baseline cytogenetic and molecular abnormalities.

2.1 **BACKGROUND**

2.1.1 **Acute myeloid leukemia**

Approximately, 30-40% of adults with AML fail to achieve CR with 1 or 2 cycles of induction chemotherapy, and are deemed primary refractory. The outcomes of patients with acute myeloid leukemia (AML) who are refractory to induction therapy are dismal, with low

response rates to salvage chemotherapy and poor long-term survival¹⁻³. We have previously reported a dismal median OS of 3.8 months for patients with AML who are refractory to HiDAC-containing induction therapy (defined as $\geq 1\text{gm/m}^2$ cytarabine per dose)². Salvage therapy in such patient populations yielded a response rate of 18% and median response duration of 9 months.

These results emphasize the need to explore alternate salvage regimens for patients with relapsed/refractory AML. The development of novel and effective anti-AML agents and/or combinations is crucial to improving the outcome of AML.

2.1.2 Relapsed/Refractory AML:

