7.1.6 Pretreatment optional correlative studies (see below)

7.1.7 Electrocardiogram (EKG)

7.1.8 Routine urinalysis

7.1.9 Chest X-ray

7.1.10 TSH, free T3, free T4, free & total cortisol

7.1.11 Respiratory PCR panel

7.2 Evaluation During Treatment

7.2.1 Physical exam at the start of each cycle (± 4 days) and documentation of all concomitant medications.

7.2.2 CBC, platelet count, differential twice weekly (± 4 days) for the first 3 cycles, then every 2-4 weeks (differential can be omitted if WBC is $\leq 0.5 \times 10^9/L$)

7.2.3 Creatinine, total bilirubin, ALT, or AST, calcium, magnesium, glucose, BUN, uric acid, fractionated bilirubin, alkaline phosphatase, sodium, potassium, chloride, bicarbonate twice weekly (± 4 days) for the first 3 cycles, then every 2-4 weeks.

7.2.4 TSH, free T3, free T4, and free & total cortisol once monthly (± 4 days) for the first 3 cycles, then every 3 months (± 4 days).

7.2.5 Bone marrow aspiration on day 28 (± 7 days), then every 1-4 cycles. Bone marrow tests can be ordered more frequently if mandated by development of peripheral blood counts. No repeat bone marrow is necessary if nonresponse or progressive disease can be unequivocally diagnosed from peripheral blood tests or, in patients with a WBC < 0.3 if the bone marrow test is considered noncontributory by the investigator at any time point.

7.2.6 Concomitant medication data will not be collected or entered into the case report form except for concomitant hydroxyurea; however, the subject's medication record will contain a list of concomitant medications.

Correlative Studies relating to immunologic response (Optional):

Tumor tissue, blood samples and bone marrow aspirate will be collected from patients under Z20160444 and will be sent to [name] lab at MD Anderson for research

purposes (described below). Patients will be consented separately on this IRB approved consent for collection of additional material. Correlative laboratory studies will be conducted under this clinical trial protocol as described below.

7.2.7 Patients may participate in the clinical study protocol irrespective of whether they choose to participate in the correlative studies. In tumor tissues, immunohistochemical studies will be performed to evaluate tumor and immunological cell markers such as CD4 and CD8 T cells. In peripheral blood, we will also evaluate tumor and immune cell populations including but not limited to CD4 and CD8 T cells in pre and post therapy samples.

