evaluations will be done at MDACC. Subsequently, the patient may have the laboratory work done at a local clinic and the results reported and filed by the MDACC research nurse for the study. The laboratory work done at the local clinic will be forwarded to the patient's attending physician at MDACC or PI of the study, who will sign off on the labs to verify that the results have been reviewed.

7.2.10 EKG beginning Cycle 2 on Day 1 (+/- 5 days) for subsequent cycles.

7.2.11 Urinalysis beginning Cycle 2 on Day 1 (+/- 5 days) for subsequent cycles.

Outside Physician Participation During Treatment

1. MDACC Physician communication with the outside physician is required prior to the patient returning to the local physician. This will be documented in the patient record.
 2. A letter to the local physician outlining the patient's participation in a clinical trial will request local physician agreement to supervise the patient's care (**Appendix F**).
 3. Protocol required evaluations outside MDACC will be documented by telephone, fax or e-mail. Fax and/or e-mail will be dated and signed by the MDACC physician, indicating that they have reviewed it. Changes in drug dose and/or schedule must be discussed with and approved by the MDACC physician investigator, or their representative prior to initiation, and will be documented in the patient record.
 4. A copy of the informed consent, protocol abstract, treatment schema and evaluation during treatment will be provided to the local physician.
 5. Documentation to be provided by the local physician will include progress notes, reports of protocol required laboratory and diagnostic studies and documentation of any hospitalizations.
 6. The home physician will be requested to report to the MDACC physician investigator all life threatening events within 24 hours of documented occurrence.
 7. All follow-up visits will be performed at MDACC.
 8. Changes in drug dose and/or schedule must be discussed with and approved by the MDACC physician investigator, or their representative prior to initiation, and will be documented in the patient record.
- 7.2.12 Patients with an objective response at completion of active study treatment will be followed for survival at MD Anderson Cancer Center (MDACC) every 3 to 6 months for up to 5 years after completion of active treatment and while still on study. If the patient

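### Duration of response, a secondary objective, is tied by name only to raw descriptive statistics, is left off the Kaplan-Meier list, and has no start, end-event or censoring rule

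*Combined protocol and SAP*

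**What the plan says.** Section 1.3 lists the endpoint beside two survival endpoints: "To determine the duration of response, disease-free survival (DFS), and overall survival".

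The Statistical Analysis Plan text that closes section 11.2 then separates them. Duration of response appears in a parenthesis among patient characteristics: "Demographic/clinical characteristics (including duration of response) and safety data of the patients will be summarized using descriptive statistics such as mean, standard deviation, median". The range is listed as well. The time-to-event sentence reads: "The distribution of time-to-event endpoints (DFS and OS) including overall survival and progression free survival will be estimated using the method of Kaplan and Meier". Duration of response is not named there.

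Section 8.0 gives criteria for response, not for how long a response lasts. Sections 7.2.12 and 9.1.4 and the footnotes to Table 6 give follow-up visits every 3 to 6 months for up to 5 years after the last dose. None of these states a start date, an end event or a censoring rule for duration of response. No section fixes a data cut-off for the analysis.

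**The concern.** Duration of response is a time-to-event quantity. Some responders may still be in response at the analysis, and section 9.1.4 foresees loss to follow-up. A raw mean, SD and range need a finished duration for every responder. Without a rule, the analyst either counts the time observed so far as the full duration or leaves ongoing responses out. Both choices shorten the mean, and by different amounts, so two analysts could follow section 11.2 faithfully and report different values from the same data.

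Readers take duration of response together with ORR to judge whether responses last. As planned, the reported figure would depend on the analysis date and on an unstated choice, as well as on the treatment. The primary analysis and the stopping rules in Tables 7 and 8 do not use it.

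**Working it through.** The plan states no figure for duration of response, so there is none to reproduce. The text check is the finding; the arithmetic below only shows what could follow from it.

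**Responders.** At the 30% target ORR, 0.30 x 40 = 12 in phase II. The analysis set is wider ("All patients who received any dose of the study agent will be included in the analysis for efficacy and safety"), so with the lead-in cohorts 0.30 x 52 = 15.6 to 0.30 x 58 = 17.4, or about 16-17. The wider figure applies the phase II target to lead-in patients, some of whom may be at other dose levels.

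**Assumptions not in the documents.** Durations are exponential with median m = 6, 9 or 12 months. Section 2.1.1 reports for earlier salvage therapy that it "yielded a response rate of 18% and median response duration of 9 months"; this sets the scale only and is not a design value. Follow-up after response is either exactly 60 months or uniform over (a, b).

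**Formulas.** Let L = ln 2 / m, so the true mean is 1/L (12.98 months for m = 9).
- Observed time counted as complete: the mean is (1/L) x (1 - censored fraction), so the proportional shortfall equals the censored fraction.
- Censored fraction: exp(-60L) for a full 60 months; (exp(-La) - exp(-Lb)) / (L(b - a)) for uniform follow-up.
- Ongoing responses dropped, full 60 months: with S = exp(-60L), the shortfall is 60L x S / (1 - S). For uniform follow-up it was simulated.

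**Worked cases, m = 9 (L = 0.0770).**
- 60 months: S = 2^(-60/9) = 0.0098, so 1.0% if counted as complete; 4.62 x 0.0098 / 0.9902 = 4.6% if dropped.
- 12-60 months: (0.397 - 0.010) / (0.0770 x 48) = 10.5%.
- 3-24 months: (0.794 - 0.157) / (0.0770 x 21) = 39.3%, allowing for rounding.

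| Follow-up after response (months) | Shortfall of mean, counted as complete (m = 6/9/12) | Shortfall of mean, ongoing dropped |
|---|---|---|
| 60 for every responder | 0.1 / 1.0 / 3.1% | 0.7 / 4.6 / 11.2% |
| 12-60 | 4.5 / 10.5 / 16.9% | 11-31% |
| 9-33 | 12.0 / 22.8 / 32.2% | 25-50% |
| 3-24 | 26.6 / 39.3 / 48.7% | 40-63% |

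**The unstated choice.** At m = 9 the two readings give means of 11.6 and about 10.2 months with 12-60 months of follow-up, and 7.9 and about 6.0 with 3-24, against a true 13.0.

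**Median, counted as complete (m = 9).** Average sample medians for 12 and 17 responders are 9.4 and 9.3 with 12-60 months, against 9.5-9.6 and 9.4 if every response were fully observed (small samples from a skewed distribution average slightly above 9). With 3-24 months they fall to about 6.8. If ongoing responses are dropped, the large-sample median is 7.7 with 12-60 months and 4.8 with 3-24.

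**Kaplan-Meier comparison.** With 17 responders and 3-24 months the Kaplan-Meier median averages 9.4 where it is reached; it is not reached in 4% of simulated trials.

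**The case against.** Four arguments can be made for the plan.

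- *The wording is open.* The descriptive list is introduced as examples and includes a median, which Kaplan-Meier can supply. The time-to-event sentence is loosely drafted: it adds PFS to a parenthesis that names only DFS and OS. A reader might infer that the plan commits to ignoring censoring; the text does not go that far. What remains is that the only method attached to this endpoint by name is the descriptive one, and open wording supplies no event or censoring rule.
- *Planned follow-up is long.* A responder followed to plan has more than 60 months after response, and there the shortfall is small. This stands. A reader might infer a bias of a quarter to a half from the 3-24 month rows; no section plans such a cut, and none excludes it.
- *DFS, OS and PFS have no written rules either.* True, and the gap is therefore wider than this endpoint. But those three are at least given a method that handles censoring.
- *Relapse dates will be coarse.* Marrow is examined on day 28, "then every 1-4 cycles. Bone marrow tests can be ordered more frequently", and section 7.2.8 allows wider spacing after six months. After treatment, section 7.2.12 provides an exam and blood, or a telephone call. This limits any method, raw summaries included, and Kaplan-Meier does not cure it.

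**Conclusion.** The point holds as a secondary-endpoint defect worth correcting. A named secondary objective is assigned by name to statistics that mishandle unfinished responses, and the definitions needed to compute it are absent. High confidence attaches to the text finding. The size is conditional: under the exponential assumption the shortfall in the mean runs from about 0.1-3% with full five-year follow-up counted as complete to about 27-49% with an early cut, and is larger if ongoing responses are dropped. The median counted as complete is nearly right with long follow-up and clearly short with an early cut. These are illustrations, not predictions for this trial, because the documents give neither a cut-off nor an expected duration under the combination. ORR, its credible interval and the stopping boundaries are untouched.

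**What to change.** In the Statistical Analysis Plan text of section 11.2:

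1. Delete the parenthesis that puts duration of response in the descriptive sentence, and add duration of response to the endpoints in the Kaplan-Meier sentence.
2. Define it, among responders, as time from first documented response to relapse, progression or death, whichever is first, censored at the last disease assessment if none has occurred. Progression is needed because section 11.1 counts lesser responses: "PR (partial response) + morphologic leukemia free state (MLFS)+HI within 3 months of treatment initiation". Say what evidence ends each type of response, since the documents do not define relapse or progression in measurable terms and a blast response under HI may leave blasts above 5%.
3. State how responders who start other anti-leukemia therapy are handled.
4. Report the Kaplan-Meier median with its 95% CI and the number censored.

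The cost is a few sentences and slightly more analysis work; no new visits are needed. A patient reached only by telephone and alive is censored at the last disease assessment. Relapse dates stay only as precise as the existing visits. The interval will be wide: at a median of 9 months the upper 95% limit is not estimable in about 55% (12 responders) or 46% (17) of simulated trials with 3-24 months of follow-up, and in about 3% or fewer with 12-60 months.
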